4 STUDY SCHEMA

5 BACKGROUND AND SIGNIFICANCE

5.1 Study Disease

Of the neurological symptoms seen in brain tumor patients, seizures have remained a common occurrence. In 30% of patients, seizure is the presenting symptom and another 30-50% of patients develop seizures during the disease trajectory. Furthermore, many patients with brain tumor experiencing seizures will continue to have seizures despite being on antiepileptic drug (AED).⁶ Even though there is a wide availability of anti-seizure medications, patients, in particular brain tumor patients with epilepsy, can have treatment refractory seizures. Therefore, there is a great need for newer AEDs with different novel mechanisms to treat seizures in this specific population.

5.2 Study Agent

Perampanel, a highly selective non-competitive α -amino-3-hydroxy-5-methyl-4-isoxazolepropionic acid (AMPA) type glutamate receptor antagonist, has shown efficacy in a randomized phase III study for refractory partial-onset seizures.⁷ For most brain tumor patients suffering from seizures, the most common type is partial-onset seizures, which can be either simple or complex. The use of AMPA type glutamate receptor inhibition is particularly intriguing in that glutamate release appears to be responsible for epileptic activity in murine glioma models.⁸ Tissue isolated from tumor bearing mice exhibited increased glutamate release and presented with peritumoral hyperexcitability.⁹ Therefore, perampanel appears to be a viable candidate for seizure treatment in patients with brain tumors from both a clinical and a biological perspective.

5.2.1 Pre-clinical experience

Not applicable

5.2.2 Clinical experience

Perampanel is currently FDA-approved for the adjunctive treatment of refractory partial seizures in patient \geq 12 years of age. In a pooled analysis of three phase III studies involving 1,478 patients, median change in partial seizure frequency was greater with perampanel in comparison to placebo.² Specifically, median change in partial seizure frequencies was as follows: perampanel 4 mg, -23.3%; perampanel 8 mg, -28.8%; perampanel 12 mg, -27.2%; and placebo, -12.8%. Moreover, 50% responder rates were as follows: perampanel 4 mg, 28.5%; perampanel 8 mg, 35.3%; perampanel 12 mg, 35.0%; and placebo, 19.0%. In this pooled analysis, perampanel was well tolerated with the most frequent treatment-emergent adverse events (TEAEs) being dizziness, somnolence, and headache. Of note, there were no deaths reported and no clinically meaningful mean change in laboratory values, electrocardiography (ECG) findings, or vital signs.¹⁰ TEAEs from the pooled analysis are listed in the table below for perampanel dose 2 mg to 12 mg and placebo.

Adverse Event, n (%)	Placebo (n=442)	Perampanel 2 mg (n=180)	Perampanel 4 mg (n=172)	Perampanel 8 mg (n=431)	Perampanel 12 mg (n=255)
Any TEAE	294 (66.5)	111 (61.7)	111 (64.5)	350 (81.2)	227 (89.0)
Dizziness	40 (9.0)	18 (10.0)	28 (16.3)	137 (31.8)	109 (42.7)
Somnolence	32 (7.2)	22 (12.2)	16 (9.3)	67 (15.5)	45 (17.6)
Headache	50 (11.3)	16 (8.9)	19 (11.0)	49 (11.4)	34 (13.3)
Fatigue	21 (4.8)	8 (4.4)	13 (7.6)	36 (8.4)	31 (12.2)
Irritability	13 (2.9)	7 (3.9)	7 (4.1)	29 (6.7)	30 (11.8)
Nausea	20 (4.5)	4 (2.2)	5 (2.9)	25 (5.8)	20 (7.8)
Fall	15 (3.4)	2 (1.1)	3 (1.7)	22 (5.1)	26 (10.2)
Nasopharyngitis	18 (4.1)	7 (3.9)	9 (5.2)	23 (5.3)	11 (4.3)
Upper respiratory	12 (2.7)	11 (6.1)	6 (3.5)	14 (3.2)	10 (3.9)

tract infection					
Ataxia	0 (0.0)	0 (0.0)	1 (0.6)	14 (3.2)	21 (8.2)
Balance disorder	2 (0.5)	0 (0.0)	0 (0.0)	22 (5.1)	8 (3.1)

Most TEAEs were mild to moderate and appeared to be dose related. From the pooled analyses, discontinuation of perampanel at 4 mg was 2.9%, at 8 mg was 7.7%, and at 12 mg was 19.2% in comparison to placebo.¹⁰ Common discontinuation TEAEs were dizziness, convulsion, and somnolence.

Behavioral and psychiatric TEAEs are very important to consider with AEDs as several AEDs carry boxed warning for serious or life-threatening psychiatric and behavioral adverse reactions. Perampanel carries a similar warning to other AEDs and monitoring is recommended for serious or life-threatening psychiatric and behavioral adverse reactions including but not limited to suicidal ideation and homicidal ideation.¹⁰ In the pooled analyses, there were three serious cases of aggression and one case of suicidal ideation. Perampanel is classified as a schedule III controlled substance as it causes euphoria in selected patients from phase III clinical trials.⁷

5.3 Study Purpose/Rationale

The new generation of AEDs that are devoid of P450 enzyme induction properties (levetiracetam, lacosamide, etc.) are now recommended as the AEDs of choice in primary brain tumor patients, as they do not have interactions with standard chemotherapeutic agents (irinotecan, topotecan, etc.) or cancer-specific targeted agents (dasatinib, erlotinib, etc.).¹¹ Seizure control is an important component in the quality of life for both low-grade and high-grade brain tumor patients. In fact, seizure control is the most important predictor of quality of life in recurrent low-grade glioma patients.¹² Therefore, the study of newer AEDs in the brain tumor population is greatly needed. Therefore, we seek to evaluate the efficacy of perampanel as an adjunctive AED for the treatment of refractory partial onset seizures in primary glial tumor (glioma) patients.

6 OBJECTIVES AND ENDPOINTS

	Objective	Endpoint	Analysis
Primary	To determine the efficacy of perampanel as an adjunctive AED in patients with primary glioma presenting refractory partial onset seizure activity	Percentage of patients with ≥50% seizure reduction during the treatment period compared with seizure frequency before initiation of perampanel (i.e. 50% responder rate)	See Section 13.4
Secondary	To assess the safety and tolerability of perampanel as an adjunctive AED in patients with primary glioma presenting with refractory partial onset seizure activity	The percentage of patients who experience a adverse event possibly, probably, or definitely attributable to perampanel treatment	See Section 13.5
Exploratory	To evaluate the effect that perampanel has on neurocognition and patient-reported outcomes of quality of life (QoL) in patients with primary glioma presenting with refractory partial onset seizure activity	Mean change from baseline for each neurocognitive and QoL subscale score at each follow-up assessment	See Section 13.6

7 INVESTIGATIONAL PLAN

7.1 Study Design

This is a Phase 4 single-arm study assessing the efficacy of perampanel as an adjunct anti-epileptic drug (AED) in patients with primary glioma presenting refractory partial onset seizure activity (defined as 3 or more seizures in a 28-day period). All primary glioma patients that have refractory partial onset seizures can be considered for this clinical trial if they meet the eligibility criteria. This will include patients that are receiving active chemotherapy, which could include, but is not limited to, the following agents: temozolamide, bevacizumab, irinotecan, etoposide, lomustine, carboplatin. All concomitant medications will be recorded during the study. The study will enroll approximately 71 patients at the PRTBTC at Duke.

Perampanel will be given according to FDA-approved guidelines over a 24-week period. Patients will be started on a dose of 2 mg daily taken orally at bedtime for 2 weeks. At the start of week 3 Perampanel will be titrated up in dose in 2mg increments per week up to 8mg daily, as long as it is well tolerated by the patient. Weeks 1 and 2, patients will take 2mg, Week 3 they will take 4 mg, Week 4 they will take 6mg and starting at week 5 they will take 8mg. Highest dose will be 8 mg orally at bedtime. Starting at week 5, patients will begin the treatment period, which goes from day 1 of Week 5 through day 7 of Week 16. Patients will be assessed in the Brain Tumor Center Clinic every 8 weeks. Assessments will be made at enrollment, 8 weeks, 16 weeks, and 24 weeks. Assessments will include history, physical examination, neurological examination, evaluation of seizure history, patient-reported outcomes of quality of life, and neurocognitive testing using CNS Vital Signs®. After a total of 16 weeks on therapy, perampanel will be tapered down. At Week 17, patients will begin taking 6mg of perampanel, Week 18 4mg, Week 19 2mg, and Week 20 they will no longer take perampanel. Patients will be considered off treatment at the end of week 20, once perampanel has cleared their system. The planned treatment dose is 8mg, but the dose can be modified by the physician based on patient reported tolerability. Titration and taper periods will be determined by the physician in the case where patients do not reach the planned treatment dose of 8 mg daily. Patients will continue to take their original AED regimen after they stop perampanel. Patients will then be monitored through Week 24. Patients will remain on their original AED regimen during this treatment time and the dose of their original AED at the start of the study will not be changed while they are on study. If seizure control is achieved during the treatment period or if seizures occur during the tapering period, patients can be continued on perampanel per the discretion of the treating physician. In this instance, perampanel will be prescribed by the treating physician and not provided within the confines of the study. As is standard procedure at the PRTBTC, patients will be given a log to record the number of seizures that occur. Research team members will regularly contact patients for reminders and reports from the log.

7.1.1 Missed Doses

Patients will have a dedicated clinical research nurse and coordinator who will schedule all of their appointments and a calendar will be provided to the patients. If a patient misses a dose of perampanel medication, the PI of the study will assess each situation with the research team. If the number of missed doses is less than 3, then the patient can remain on study and perampanel will continue to be given by the study protocol regimen. If the patient misses more than 3 doses of perampanel, they will no longer remain on the clinical trial. Patients will be given daily medication logs to record the date and time that they take each dose of perampanel, as well as their other AEDs.. At each study visit, they will be asked about all medications that they are taking.

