7.1.3 Study Drug Blinding

Not applicable.

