7.4 Definition of Evaluable Subjects, On Study, and End of Study

All patients who complete the treatment period will be included in the primary endpoint analysis. All patients who received protocol treatment, regardless of duration, will be included in the safety analysis.

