10.7 Early Withdrawal of Subject(s)

10.7.1 Criteria for Early Withdrawal

Subjects may voluntarily withdraw from the study at any time. The PI may also withdraw a subject from the study at any time based on his/her discretion. Reasons for PI-initiated withdrawal may include, but is not limited to the following:

- Pregnancy
- Upon request of the subject
- If, in the investigator's medical judgment, further participation would be injurious to the subject's health or wellbeing
- Development of intolerable symptoms
- Non-compliance of the subject
- Development of any exclusion criteria

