13.1 Analysis Sets

As indicated in section 7.4, subject to the availability of data, all patients who receive perampanel treatment will be included in safety analyses. All patients who complete the treatment period of the study will be included in efficacy analyses.

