13.4.2 Statistical Hypothesis, Model, and Method of Analysis

As described in Section 3.5 and 13.8, this study has been designed to detect an increase in the 50% responder rate from a benchmark of 20% to 35%. A one-sample binomial test will test this hypothesis at the 0.1 level of significance.

As a related secondary analysis, seizure frequency will be estimated separately for each patient within the titration, treatment, tapering, and follow-up phases of treatment, and the percent reduction in seizure frequency relative to baseline computed. The distribution across patients within each treatment phase in the percent reduction will be described. Depending upon the distribution of these data, means and standard deviations may be used to describe the distribution of percent reduction or quartiles.

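### Exactly 3 missed doses falls in neither branch of 7.1.1, and removal under that rule before the treatment period ends also takes the patient out of the primary analysis

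*Combined protocol and SAP*

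**What the plan says.** Section 7.1.1 has two branches. The first is "If the number of missed doses is less than 3, then the patient can remain on study". The second is "If the patient misses more than 3 doses of perampanel, they will no longer remain on the clinical trial". Ahead of both stands a case-by-case step: "If a patient misses a dose of perampanel medication, the PI of the study will assess each situation with the research team". The section does not say whether misses are counted over the whole study, within a dosing period, or consecutively.

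The analysis sets depend on completion. Section 7.4: "All patients who complete the treatment period will be included in the primary endpoint analysis". Section 13.1: "All patients who complete the treatment period of the study will be included in efficacy analyses". Early withdrawals are not replaced (10.7.3), and Section 13 describes neither an all-treated analysis nor a sensitivity analysis for non-completers.

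There is no blinding (7.1.3), and under 7.1 the research team contacts patients regularly for seizure-log reports.

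**The concern.** Below 3 and above 3 do not cover 3. For a patient with exactly 3 missed doses, the only instruction left is the PI's individual assessment, and the PI and team can know that patient's seizure course when they make it.

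This would be an operational detail if the patient were analysed either way. Under 7.4 and 13.1 the patient is not: someone taken off the trial before the end of the treatment period drops out of the primary analysis. Membership of that set therefore depends on adherence after baseline, which may be related to tolerability or response. At exactly 3 misses it also depends on a decision that can be taken with the outcome in view. The test compares one responder proportion with a fixed 20% benchmark, and no control arm is subject to the same selection. Losing non-responders from the denominator raises the observed proportion directly.

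**Working it through.** **1. The plan's own figure.** Inputs from 13.4.2 and 13.8: null rate 0.20, alternative 0.35, type I error 0.1, power 90%, 61 evaluable, 71 enrolled. The plan says only "A one-sample binomial test will test this hypothesis at the 0.1 level of significance" and does not state sidedness. One-sided is assumed here because it reproduces 61. With N = 61 the smallest success count is 17:

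- P(X ≥ 17 | 61, 0.20) = 0.088
- P(X ≥ 17 | 61, 0.35) = 0.905

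At N = 60 power is 0.890, so 61 agrees with the stated 90%.

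**2. How many patients could be affected.** The documents give no adherence figure, so the daily miss probability q is an assumption. Misses are taken as independent over Weeks 1 to 16, that is 16 × 7 = 112 doses.

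P(exactly 3) = C(112,3) q³ (1 − q)¹⁰⁹, with C(112,3) = 227,920. At q = 0.01 this is 227,920 × 0.000001 × 0.99¹⁰⁹ = 0.076.

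| q per day (assumed) | exactly 3 | of 71 | more than 3 | of 71 |
|---|---|---|---|---|
| 0.5% | 1.6% | 1.2 | 0.3% | 0.2 |
| 1% | 7.6% | 5.4 | 2.7% | 1.9 |
| 2% | 20.2% | 14.3 | 18.7% | 13.3 |

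The counting window matters because it is not stated. Over 84 doses the exactly-3 shares are 0.8%, 4.2% and 14.8%. Eighty-four doses is Weeks 1 to 12 or Weeks 5 to 16. Section 3.2 ends the treatment period at Week 12 and 7.1 ends it at Week 16, so the point of completion is itself unsettled.

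**3. Whether a few exclusions can change the conclusion.** Take 16 responders, one short of success at N = 61, and remove non-responders one at a time. One-sided P(X ≥ 16 | n, 0.20):

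- n = 61: 0.146
- n = 60: 0.131
- n = 59: 0.116
- n = 58: 0.103
- n = 57: 0.091, significant at 0.1

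**4. Worst-case type I error.** Suppose k of the 61 have exactly 3 misses, every non-responder among them is excluded and every responder is kept. Up to k = 3 the type I error stays at 0.088. At k = 4, success is also reached when there are 16 responders and all four affected patients are non-responders. That adds P(X = 16 | 57, 0.20) × 0.8⁴ = 0.0404 × 0.4096 = 0.0165, giving 0.0879 + 0.0165 = 0.104. At k = 5 it is 0.123. This is an upper bound on the harm, not a forecast.

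**The case against.** **Wider discretion exists anyway.** Section 10.7.1 states "The PI may also withdraw a subject from the study at any time based on his/her discretion" and lists non-compliance as a reason. Closing the gap at 3 would leave that untouched. This stands. A reader might infer that the gap by itself settles who is in the primary analysis. It does not: it concerns patients at exactly 3 misses, and only when the decision falls before the treatment period ends. Above 3, removal is fixed by rule. The objection argues for changing the analysis set as well as the wording.

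**The size is uncertain.** A reader might expect 3 misses to be common over 16 weeks of daily dosing. Nothing in the documents supports that, and at 0.5% per day it is about one patient. At higher rates the unambiguous branch matters as much or more: at 3% per day, more than 3 misses occurs in 43% of patients and exactly 3 in 22%. This stands too.

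**Power loss is a weak argument.** One might subtract 14 affected patients from about 60 evaluable, reach 46 and quote 79% power. That mixes denominators, since the 14 are out of 71 enrolled. Twenty per cent of 60 is 12, leaving 48 with power 84%, and only if every such patient is removed. If they stay, nothing is lost.

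**Timing limits the effect.** Section 8.4 has medication logs reviewed at study visits, which fall at Weeks 8, 16 and 24. If misses are found only then, the decisions that clearly precede completion at Week 16 rest on the first 56 doses, where exactly 3 occurs in 0.3%, 1.6% or 7.6% at the three rates (about 0, 1 or 5 of 71). This is a fair reduction, but the protocol does not say that misses are acted on only at visits.

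**Conclusion.** The concern holds in bounded form. The missing value is plain on the face of 7.1.1, no other section supplies it, and the link to the primary endpoint through 7.4 and 13.1 is explicit. Primary-set membership depends on post-baseline adherence for anyone removed under 7.1.1 before the treatment period ends. At exactly 3 misses it also depends on an unblinded individual decision.

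On the assumed rates of 0.5% to 2% per day over 112 doses, about 1 to 14 of 71 patients would reach exactly 3, and fewer if the counting window is shorter. Four selective exclusions are enough to turn a near miss into a positive result. With three or fewer affected patients, even the worst case keeps type I error below 0.10. The documents show that bias is possible. They do not show that it will occur, in what amount, or that 61 is the wrong sample size. The point is worth fixing because the fix is cheap and makes the primary result independent of the decision.

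**What to change.** 1. **Section 7.1.1.** The sponsor-investigator should reconcile the two sentences so that every count falls in exactly one branch, and state the period over which misses are counted. Which branch applies at 3 is a clinical matter, and no threshold is proposed here.
2. **Sections 7.4 and 13.1, both.** State that removal under 7.1.1 does not remove a patient from the primary efficacy set. Changing only 13.1 would leave it in conflict with 7.4.
3. **Scoring.** Score patients with treatment-period days on perampanel by the 13.4.1 rate over those days, since that definition already divides by days of administration. Patients removed during titration have no such days and need a prespecified rule. Keep the completer analysis as supportive.

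**Cost.** A few sentences. The daily medication log already gives the count, and 10.4 already asks patients who withdraw early to complete the end-of-treatment procedures, which include seizure-log collection. The responder rate may be somewhat lower, and rates for patients removed early rest on fewer days.

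The scoring rule must be explicit because the cost depends on it. If all 16% of non-completers were instead counted as non-responders among 71 treated, the expected rate would be 0.35 × 0.84 = 0.294. Power would then fall to about 0.63 (success at 20 or more, type I error 0.062), and the sample size would need to be revisited.

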7.1.2 Concomitant Medications

With concomitant use, perampanel, at a dose of 12 mg/day, reduced levonorgestrel exposure by approximately 40%. Use of perampanel with oral or implant contraceptives containing levonorgestrel may render them less effective. Therefore, additional non-hormonal forms of contraception are recommended (please see the FYCOMPA FDA-approved labeling dated 2/12/2014).¹

The concomitant use of known CYP enzyme inducers including carbamazepine, phenytoin, or oxcarbazepine with perampanel decreased the plasma levels of perampanel by approximately 50~67%. The starting doses for perampanel should be increased in the presence of enzyme-inducing AEDs.¹ When these enzyme-inducing AEDs are introduced or withdrawn from a patient's treatment regimen, patient should be closely monitored for clinical response and tolerability. As noted, however, the decrease in the therapeutic effect seen in patients on concomitant treatment, was not affected by use of higher doses (8 mg to 12 mg).¹

Concomitant use of perampanel with other strong CYP3A inducers (e.g., rifampin, St. John's wort) should be avoided.¹

The concomitant use of perampanel and CNS depressants including alcohol may increase CNS depression.¹ A pharmacodynamic interaction study in healthy subjects found that the effects of perampanel on complex tasks such as driving ability were additive or supra-additive to the impairment effects of alcohol. Multiple dosing of perampanel 12 mg/day also enhanced the effects of alcohol to interfere with vigilance and alertness, and increased levels of anger, confusion, and depression. These effects may also be seen when perampanel is used in combination with other CNS depressants. Care should be taken when administering perampanel with these agents. Patients should limit activity until they have experience with concomitant use of CNS depressants (e.g. benzodiazepines, narcotics, barbiturates, sedating antihistamines). Advise patients not to drive or operate machinery until they have gained sufficient experience on perampanel to gauge whether it adversely affects these activities.¹

Perampanel is FDA-approved as adjunctive therapy for refractory partial onset seizures, so it will be utilized in concert with other AEDs.

If subjects are receiving chemotherapy during the study, these medications, the doses, and any associated serious adverse events will be recorded.

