3.3 Selection of Subjects

Inclusion Criteria:

1. Patients must be diagnosed with a primary glioma and have refractory partial onset seizure activity (defined as 3 or more seizures in a 28-day period) on non-enzyme inducing anti-epileptic regimen that can

include, but not limited to the following: levetiracetam (Keppra) or Keppra XR, lamotrigine (Lamictal) or Lamictal XR, gabapentin (Neurontin), tiagabine (Gabitril), topiramate (Topamax), valproic acid (Depakene) / valproate (Depacon), zonisamide (Zonegran), lacosamide (Vimpat), and clonazepam (Klonopin)

2. Adult patients (\geq 18 years old)
3. Karnofsky \geq 70%
4. Hematocrit \geq 29%, ANC \geq 1,500 cells/L, platelets \geq 100,000 cells/L
5. Serum creatinine \leq 1.5 mg/dL, serum AST and bilirubin \leq 1.5 times the upper limit of normal
6. If sexually active, patients will take contraceptive measures for the duration of protocol treatment and continue until two months after treatment. The effectiveness of hormonal contraceptives containing levonorgestrel has been shown to be reduced by perampanel at a 12 mg dose.¹ Therefore, alternative or back-up methods of contraception are recommended.
7. Signed informed consent approved by the Duke Institutional Review Board

Exclusion Criteria:

1. Pregnant or breastfeeding (Both perampanel and levetiracetam are classified as Pregnancy Category C drugs.)
2. Chronic excessive use of psycho-pharmaceuticals, alcohol, illicit drugs, or narcotics
3. Inability to complete or perform measures of patient-reported outcomes or neurocognitive testing on the computer
4. Known allergy to perampanel
5. Concomitant use of known cytochrome P450 (3A4,5,7) inducers such as carbamazepine, phenytoin, or oxcarbazepine (see Appendix A)
6. Previous history of suicidal ideation, homicidal ideation, depression leading to hospitalization or mood disturbance leading to hospitalization.

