10.3 Treatment Period

Day 1

- Subjects will be started on a dose of 2 mg of perampanel daily taken orally at bedtime for 2 weeks.
- Subjects will then be titrated up in dose in 2 mg increments each week up to 8 mg daily. Week 3 4mg daily, Week 4 6 mg daily and starting week 5 8 mg daily. The highest dose of perampanel will be 8 mg orally at bedtime.

Week 8 assessments) (+ 1 week)

- History and physical exam, including KPS and a full neurologic assessment, with collection of seizure log (subjects will keep a seizure log throughout the study)
- Toxicity assessment using CTCAE v.4 guidelines (continuous throughout study)
- CBC with diff
- CMP
- Quality of life measurements and neurocognitive testing

Week 16 assessments) (+ 1 week)

- After a total of 16 weeks on therapy, subjects will now be tapered off of perampanel over a period of 4 weeks. Week 17 6mg daily, Week 18 4mg, Week 19 2mg, and at Week 20 they will no longer take perampanel. (
- History and physical exam, including KPS and a full neurologic assessment, with collection of seizure log (subjects will keep a seizure log throughout the study)
- Toxicity assessment using CTCAE v.4 guidelines
- CBC with diff
- CMP
- Quality of life measurements and neurocognitive testing

Week 24 assessments- End of Treatment) (+ 1 week)

- History and physical exam, including KPS and a full neurologic assessment, with collection of seizure log (subjects will keep a seizure log throughout the study)
- Toxicity assessment using CTCAE v.4 guidelines
- CBC with diff
- CMP
- Quality of life measurements and neurocognitive testing
- Toxicity assessment using CTCAE v.4 guidelines (continuous throughout study)

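### A patient who adds an anti-epileptic drug for worsening seizures has no scoring rule: the plan lets that patient leave the denominator or count as a perampanel responder, and its text on enzyme inducers does not settle which

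*Combined protocol and SAP*

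**What the plan says.** **Background AEDs.** Sections 3.2 and 7.1 say that patients stay on their original AED regimen, at an unchanged dose, while on study. Inclusion criterion 1 (3.3) requires that patients be "on non-enzyme inducing anti-epileptic regimen that can" include the drugs it lists. Neither 3.2 nor 7.1 says what follows if an AED is added.

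**Inducers.** Exclusion criterion 5 (3.3) names "Concomitant use of known cytochrome P450 (3A4,5,7) inducers such as carbamazepine, phenytoin, or oxcarbazepine (see Appendix A"). Section 10.7.1 lists "Development of any exclusion criteria" among the grounds on which the investigator can withdraw a patient, but the list is permissive: "Reasons for PI-initiated withdrawal may include, but is not limited to the following".

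**Concomitant medications.** Section 7.1.2 discusses the same three inducing AEDs as drugs that may come and go during treatment: "When these enzyme-inducing AEDs are introduced or withdrawn from a patient's treatment regimen, patient should be closely monitored for clinical response and tolerability". It also says: "The starting doses for perampanel should be increased in the presence of enzyme-inducing AEDs". Section 3.4 carries nearly the same text and adds that perampanel dose adjustment may be needed; that sentence is absent from 7.1.2. Neither section refers to the exclusion criterion or to withdrawal.

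**Analysis.** Section 13.1: "All patients who complete the treatment period of the study will be included in efficacy analyses". Section 7.4 says the same for the primary endpoint, and 10.7.3 provides no replacement of early withdrawals. Section 13.4.1 computes on-treatment seizure frequency as seizures while on perampanel in the treatment period divided by days on perampanel. It does not mention other AEDs.

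**The concern.** Needing a further AED for worsening seizures is itself evidence that perampanel has not controlled them. The plan does not treat it as an outcome. What happens to the patient depends on a discretionary decision, taken with the seizure course known, in a trial with no control arm to absorb the effect.

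- If the patient is withdrawn, a likely non-responder leaves the denominator.
- If the patient is kept, any later control is credited to perampanel although another drug was added.

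Inducers are where the text is least settled, because one part of the protocol excludes them and another describes monitoring when they are introduced. The analysis gap is the same for a non-inducing add-on. At stake is the single primary comparison, a responder rate tested against a fixed 20% benchmark.

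**Working it through.** **Inputs.** Benchmark 20%, target 35%, significance level 0.1, power 90%, 61 evaluable patients, 71 enrolled (3.5, 13.8); one-sample binomial test (13.4.2). The plan does not state sidedness; one-sided is used here because it reproduces the stated sample size.

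**Step 1: reproduce the plan's figure.** The cut-off c is the smallest value with P(X ≥ c | n, 0.20) ≤ 0.10. For n = 61, c = 17: P(X ≥ 17 | 61, 0.20) = 0.088 and P(X ≥ 17 | 61, 0.35) = 0.906. No smaller n meets both limits, so 61 is confirmed.

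**Step 2: drop patients who added an AED.** Suppose 16 of 61 respond, and k of the non-responders added an AED and are withdrawn. The p-value is P(X ≥ 16 | 61 − k, 0.20).

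| k | Result | Rate | p | Cut-off | Success? |
|---|---|---|---|---|---|
| 0 | 16/61 | 26.2% | 0.146 | 17 | no |
| 1 | 16/60 | 26.7% | 0.131 | 17 | no |
| 2 | 16/59 | 27.1% | 0.116 | 17 | no |
| 3 | 16/58 | 27.6% | 0.103 | 17 | no |
| 4 | 16/57 | 28.1% | 0.091 | 16 | yes |

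**Step 3: keep them.** If one of those patients stays on study and is controlled after the added AED, the count is 17/61 = 27.9%, p = 0.088, a success.

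**Step 4: the same point within the plan's own attrition.** The 61 is what should remain after early discontinuations from 71. Suppose 17 of 61 completers respond (a success), and two of the discontinued patients left after adding an AED for seizures. Returned as non-responders, they give 17/63 = 27.0%, p = 0.112, against a cut-off of 18: not a success. With one returned, 17/62 gives p = 0.0995, which still succeeds.

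**Step 5: chance of a false success.** Let the true rate be exactly 20% (0.20 × 61 = 12.2 expected responders), with k patients who would be non-responders without the added AED.

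- Counted as non-responders: 0.088 for any k.
- Dropped, P(X ≥ c | 61 − k, 12.2/(61 − k)): about 0.087 for k = 1 to 3, 0.144 for k = 4, 0.143 for k = 6, 0.221 for k = 10. The rise comes in steps because the cut-off is a whole number.
- Kept, with every one counted as a responder, P(X ≥ 17 | 61, (12.2 + k)/61): 0.239 for k = 2 and 0.456 for k = 4. This is an upper bound.

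**Direction.** With x responders, x/(n − k) is greater than x/n whenever x > 0, and a kept patient adds either 0 or 1 to x. Compared with scoring these patients as non-responders, neither route can lower the rate.

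**The case against.** The strongest reply is that the protocol already governs this case. Patients are to keep their original regimen, and that regimen must be non-inducing, so starting phenytoin in week 8 would be a departure. The text in 7.1.2 and 3.4 cites the prescribing information and reads as restated labeling. All of this is fair. It explains how the inconsistency arose, but it does not say how a departure is scored.

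Four stronger readings are tempting, and the documents do not support them.

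- *That 7.1.2 permits the patient to stay on study.* It asks only for close monitoring, which is compatible with withdrawal under 10.7.1. It is silent on both study status and analysis.
- *That one patient faces two starting-dose instructions.* Section 10.3 says: "Subjects will be started on a dose of 2 mg of perampanel daily taken orally at bedtime for 2 weeks". This differs from the starting-dose sentence in 7.1.2, but anyone on an inducer on Day 1 is ineligible, so no eligible patient receives both instructions. The point is one of wording.
- *That every retained patient inflates the result.* The 13.4.1 ratio includes the seizures before the AED was added. By the protocol's own account, inducers cut perampanel levels by about 50 to 67%. Such a patient may well remain a non-responder.
- *That the bias is known to be large.* The documents describe no rescue AED and give no frequency of AED additions. The example in steps 2 and 3 starts one responder short of success, and fewer than four removals do not alter its result.

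It is also true that the denominator loss comes from the completer-only set rather than from inducers as such. For that reason the scoring rule should cover any AED added for seizure control.

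**Conclusion.** The point holds as a gap in the primary analysis, accompanied by unreconciled text on inducers. The plan has no rule for a patient who adds an AED for worsening seizures, and both available outcomes give a responder rate equal to or higher than scoring that patient as a non-responder. The size is unknown because it depends on how many patients do this. One to three dropped patients leave the false-success probability near 0.087. Four raise it from 0.088 to about 0.144, and two retained patients could raise it to 0.239 at most. These figures assume a one-sided exact test, a true rate of 20% and patients who would not have responded without the added drug. The change is worth making because it is cheap and the direction is clear. The documents do not show that the trial's conclusion would change.

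**What to change.** 1. Reconcile 3.2, 3.3, 3.4, 7.1, 7.1.2 and 10.7.1 so that they give one consistent account of an enzyme inducer at entry and one started on study. The clinical rule is for the sponsor to decide.
2. Add to 13.4.1, with matching wording in 7.4 and 13.1: *A patient who starts any additional AED (enzyme-inducing or not) for seizure control after the first dose of perampanel and before the end of the treatment period stays in the primary-analysis denominator and is counted as a non-responder.*
3. State that an inducer started for another reason is not scored as a seizure failure. Report those patients and handle them in a sensitivity analysis.
4. State that the binomial cut-off is computed for the number of patients actually in the denominator.

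**Cost.** Protocol wording and a short addition to the analysis section. No new data are needed: concomitant medications are recorded (7.1) and patients log their AEDs daily (7.1.1, 8.4). The reason for starting a drug should be captured with the entry so that the rule can be applied. The observed responder rate may be slightly lower. Scoring as non-response is not the only defensible choice, but it is simple and fits a test against a fixed benchmark.
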